#### **4.2.1.4. Additional Inclusion criteria specific for subjects with chronic spontaneous urticaria (Part C)**

Subjects will be included in the chronic spontaneous urticaria cohort if all the following criteria apply

1. The subject is aged between 18 and 70 years of age inclusive, at the time of signing the informed consent.
2. Body weight  $\geq$  50 kg and BMI within the range 19 to 35 kg/m^2 (inclusive)
3. Subjects who have a score of  $>14$  on the UAS7 questionnaire with between 4-20 weals observed in a defined area of the body will be included in this study. This area must include either arms, legs or torso for 7 consecutive days during the screening period, prior to the Day 1 visit. If a subject has not completed 7 consecutive days of UAS questionnaire prior to dosing on Day 1 due to exceptional circumstances, the screening period may be extended until the subject has completed 7 consecutive days of UAS questionnaire. This will only be at the discretion of the Investigator.
4. No other aetiology identified for chronic urticaria such as drug-related or inducible urticaria as determined by history, physical examination and laboratory studies.
5. Subjects must be free from any past or present benign or malignant skin conditions and disease, other than the specified condition required for eligibility of subjects as defined in the specific inclusion criteria for CsU cohort unless in the opinion of the investigator it will not compromise the subjects safety and quality of data.

6. Other than a diagnosis of chronic spontaneous urticaria the subject should have no other co-morbidities which would introduce additional risk factors and will not interfere with the study procedures, as determined by a responsible and experienced physician, based on a medical evaluation including medical history, physical examination, laboratory tests and cardiac monitoring.
7. A subject with a clinical abnormality or laboratory parameter(s) which is/are not specifically listed in the inclusion or exclusion criteria, outside the reference range for the population being studied may be included only if the Investigator, in consultation with the GSK Medical monitor if required, agrees and documents that the finding is unlikely to introduce additional risk factors and will not interfere with the study procedures.
8. Female subjects of child bearing potential must have been using one of the contraception methods listed in Section 4.3.1 at least 28 days before their screening visit and agree to continue with these methods until the follow up visit or 12 days after the last dose of study treatment, whichever is the longer.

If a patient who has been screened and is eligible for the study becomes unavailable to do the study at initially planned dates due to exceptional circumstances, the subject may be re-screened for the study; in total a patient may be screened 2 times. This will only be at the discretion of the Investigator.

#### **4.2.2. All Cohorts Exclusion Criteria**

A subject will **not be eligible** for inclusion in this study if any of the following criteria apply:

1. TSH levels outside the normal range.
2. Subjects with a history of Graves disease.
3. Subjects with a history of any thyroid cancer.
4. Unable or unwilling to avoid use of topical creams/lotions at sites where medication will be applied. Washing with soap and water will be permitted.
5. Based on averaged QTcF values of triplicate ECGs obtained over a brief recording period:
  - QTc(F) > 450 msec; or QTc(F) > 480 msec in subjects with Bundle Branch Block.
6. ALT, alkaline phosphatase and bilirubin  $\geq 1.5 \times \text{ULN}$  (isolated bilirubin  $> 1.5 \times \text{ULN}$  is acceptable if bilirubin is fractionated and direct bilirubin  $< 35\%$ ).
7. Current or chronic history of liver disease, or known hepatic or biliary abnormalities (with the exception of Gilbert's syndrome or asymptomatic gallstones or previous history of uncomplicated cholecystectomy).
8. History of regular alcohol consumption within 6 months of the study defined as:
  - An average weekly intake of  $> 21$  units for males or  $> 14$  units for females. One unit is equivalent to 8 g of alcohol: a half-pint (~240 ml) of beer, 1 glass (125 ml) of wine or 1 (25 ml) measure of spirits.

9. History of sensitivity to any of the study medications, or components thereof, history of anaphylaxis or a history of drug or other allergy that, in the opinion of the investigator or GSK Medical monitor, contraindicates their participation.
10. Unable to refrain from vitamins, herbal and dietary supplements (including St John's Wort) within 7 days (or 14 days if the drug is a potential enzyme inducer) or 5 half lives (whichever is longer) prior to the screening visit until the completion of the follow-up assessments, unless in the opinion of the Investigator, in consultation with the GSK Medical monitor if required, the medication will not interfere with the study procedures or compromise subject safety.
11. A positive pre-study Hepatitis B surface antigen or positive Hepatitis C antibody result within 3 months of screening.
12. A positive test for HIV antibody.
13. A positive drug screen at screening or Day -1 (parts A & B only). For Part B patients, a positive drug screen due to concomitant medication may be acceptable for inclusion in the study based on the Investigator's opinion. The Investigator's opinion must be based on interview of the subject, documented in the medical history and the Investigator is asked to document that the positive test can be explained by a relevant and permitted medication (see Section 5.15.1.) and that the medication will not interfere with the study procedures or compromise subject safety. A drug screen will not be performed in Part C.
14. Lactating females.
15. Where participation in the study would result in donation of blood or blood products in excess of 500 mL within a 56 day period.
16. The subject has participated in a clinical trial and has received an investigational product within the following time period prior to the first dosing day in the current study: 30 days, 5 half-lives or twice the duration of the biological effect of the investigational product (whichever is longer).
17. Exposure to more than four new chemical entities within 12 months prior to the first dosing day
18. Use of topical steroids or calcinurin inhibitors is prohibited during the study from screening to follow up (See Section 5.12).
19. Exclusion related to prior drug treatments:
  - a) Intake of oral corticosteroids within 7 days >10mg/day prior to first screening visit.
  - b) Use of depot corticosteroids within 7 days prior to first screening visit.
  - c) Subjects who are taking anticoagulants (e.g. warfarin) must not be on warfarin within 21 days prior to screening. (See Section 5.15).
  - d) Subjects who are having psoralen combined with ultraviolet A (PUVA) treatment must not be using PUVA treatment within 21 days prior to screening.

20. Subjects who work for the Sponsor, Contract Research Organisation (CRO), or one of the study centres.

**4.2.2.1. Country Specific Exclusion criteria wording for Germany that applies to Part A, Part B and Part C**

1. Subjects who live in detention on court order or on regulatory action, see §40 subsection 1 sentence 3 no. 4 AMG. (Arzneimittelgesetz) [[MEDICINAL PRODUCTS ACT](#), 2015].

**4.2.2.2. Additional Exclusion for Part A – Healthy Subjects**

2. Use of H1 antihistamines within 3 days prior to first screening visit

**4.2.2.3. Additional Exclusion for Part B – Cold urticaria Subjects**

1. fT4, T4, T3 outside the normal range.
2. Exclusion related to prior drug treatments:
  - Use of zaditen (Ketotifen) within 14 days prior to first screening visit
  - Use of doxepin AZU and other tricyclic antidepressants with antihistaminergic properties within 14 days prior to first screening visit
  - Use of H2 antihistamines within 7 days prior to first screening visit
  - Use of H1 antihistamines within 7 days prior to first screening visit
  - Use of monteleukast or any other leukotriene antagonist within 7 days prior to first screening visit
  - Use of biologicals including omalizumab within 5 months prior to first screening visit

**4.2.2.4. Additional Exclusion for Part C- Chronic Spontaneous Urticaria patients**

1. fT4, T4, T3 outside the normal range.
2. Exclusion related to prior drug treatments
  - Intake of cyclosporin within 10 days prior to first screening visit
  - Intake of other immunosuppressant drugs within 28 days of first screening visit
  - Use of monteleukast or any other leukotriene antagonist within 7 days prior to first screening visit
  - Use of dapsone within 7 days prior to first screening visit
  - Use of zaditen (Ketotifen) within 14 days prior to first screening visit
  - Use of doxepin AZU and other tricyclic antidepressants with antihistaminergic properties within 14 days prior to first screening visit
  - Use of H2 antihistamines within 7 days prior first screening visit

- Use of biologicals including omalizumab within 5 months prior to first screening visit
- Use of H1 antihistamines above the licensed dose within 3 days prior to first screening visit

### **4.3. Lifestyle and/or Dietary Restrictions**

#### **4.3.1. Contraception Requirements**

##### **4.3.1.1. Female Subjects**

In Part A: Female subjects of non-childbearing potential will be recruited onto the study.

In Parts B and C: Female subjects of child bearing potential may be recruited onto the study, and must not become pregnant and so must be sexually inactive by abstinence or use contraceptive methods with a failure rate of < 1%. Female subjects of childbearing potential with same sex partners are not required to be abstinent or to use contraception. Subjects in parts B and C will need to be on established contraceptive as listed in Section 4.2.1 inclusion criteria at the time of screening (day -28) and will have regular serum/urine pregnancy testing throughout the duration of the study as listed in the Time and Events Table Section 6.1. Contraceptive use shall be continuous through the pre-study, study and follow-up periods of the study.

##### **Abstinence**

Sexual inactivity by abstinence must be consistent with the preferred and usual lifestyle of the subject. Periodic abstinence (e.g. calendar, ovulation, symptothermal, post-ovulation methods) and withdrawal are not acceptable methods of contraception.

##### **Contraceptive Methods with a Failure Rate of < 1%**

- Combined oral contraceptive
- Injectable progestogen
- Implants of etonogestrel or levonorgestrel
- Estrogenic vaginal ring
- Percutaneous contraceptive patches
- Intrauterine device (IUD) or intrauterine system (IUS) that meets the <1% failure rate as stated in the product label
- **Documented** male partner sterilization prior to the **female subject's entry** into the study, and this male is the sole partner for that subject. For this definition, “documented” refers to the outcome of the investigator's/designee's review of the subject's medical history for study eligibility, as obtained via a verbal interview with the subject or from the subject's medical records.
- Male condom **combined with a female** diaphragm, either with or without a vaginal spermicide (foam, gel, film, cream, or suppository) (Hatcher, 2007)

**NOTE:** These allowed methods of contraception are only effective when used consistently, correctly and in accordance with the product label. The investigator is responsible for ensuring subjects understand how to properly use these methods of contraception.

#### **4.3.1.2. Male Subjects**

Male subjects with female partners of child-bearing potential must use one of the following contraceptive methods after the first dose of study treatment and until the follow-up contact.

- Condom plus partner use of a highly effective contraceptive (see list in Section 4.3.1.1).
- Abstinence, defined as sexual inactivity consistent with the preferred and usual lifestyle of the subject. Periodic abstinence (e.g. calendar, ovulation, symptothermal, post-ovulation methods) and withdrawal are not acceptable methods of contraception

#### **4.3.2. Meals and Restrictions**

##### **4.3.2.1. Caffeine, Alcohol, and Tobacco**

###### **Healthy volunteers (Part A)**

- Will abstain from ingesting caffeine- or xanthine-containing products (e.g. coffee, tea, cola drinks, chocolate) and alcohol for 24 hours prior to the start of dosing until collection of the final pharmacokinetic and/or pharmacodynamic sample

###### **Subjects with Cold urticaria (Part B)**

- Will abstain from ingesting caffeine- or xanthine-containing products (e.g. coffee, tea, cola drinks, chocolate) and alcohol for 24 hours prior to the start of dosing until discharge from the research unit.

###### **Subjects with Chronic spontaneous urticaria (Part C)**

- Will be allowed alcohol (an average weekly intake of <21 units for males or <14 units for females).
- There are no caffeine, or tobacco restrictions for patients with chronic spontaneous urticaria.

##### **4.3.2.2. Fasting**

- Subjects will be required to be fasted prior to the screening visit.

##### **4.3.3. Activity and other restrictions during the study**

Subjects will abstain from strenuous exercise for 48 hours prior to each blood collection for clinical laboratory tests. Subjects may participate in light recreational activities during studies (e.g., watch television, read).

#### **4.3.3.1. Showering/bathing during the study**

In all dose cohorts, subjects will be allowed to shower/bathe approximately 2 hours prior to dosing and approximately 18-22 hours following dosing. During showering/bathing the subject should only use mild, unscented, and non-medicated soap. A mild shampoo can be used for washing hair. The site of blood sampling will be protected (taped off and covered) if required, allowing the subjects to shower freely, including washing the application site(s). Subjects should refrain from rubbing the areas where the cream has been applied.

Timings of showering/bathing must be recorded (as detailed in the SPM).

Subjects must refrain from taking part in water based activities such as swimming and use of sauna/steam room for the duration of dosing until the follow-up visit.

#### **4.3.3.2. Clothing during the study**

Subjects will be allowed to use their normal clothing for the duration of the dosing period as long as it is not tight fitting. Subjects will not be allowed to put clothing over dosed areas until 60 minutes after application of the cream.

### **4.4. Screen and Baseline Failures**

Screen failures are defined as subjects who consent to participate in the clinical trial but are never subsequently randomized. In order to ensure transparent reporting of screen failure subjects, meet the Consolidated Standards of Reporting Trials (CONSORT) publishing requirements, and respond to queries from Regulatory authorities, a minimal set of screen failure information is required including Demography, Screen Failure details, Eligibility Criteria, and any Serious Adverse Events.

#### **4.4.1. Subjects exceeding screening visit window**

Subjects in Part B and Part C that are not randomized within the allotted screening window may be re-screened once, as per Section 4.2.1. If re-screening is performed, it is essential that subjects are assigned a different unique subject ID number for the additional screening attempt. See the SPM for specific details.

### **4.5. Withdrawal Criteria and Procedures**

A subject may withdraw from study treatment at any time at his/her own request, or may be withdrawn at any time at the discretion of the investigator for safety, behavioural or administrative reasons.

Refer to Section 5.5 for planned dose adjustment/stopping criteria and Section 5.7 for subject specific dose adaptation/stopping criteria including Liver Chemistry and QTcF.

Liver chemistry threshold stopping criteria have been designed to assure subject safety and to evaluate liver event aetiology (in alignment with the FDA premarketing clinical liver safety guidance). See Section 5.7.1 for details.

## 4.6. Subject Completion

A completed subject is one who has completed all visits of the study including the follow-up visit.

The end of the study is defined as the last subject's last visit which is a follow up visit.

## 5. STUDY TREATMENT

### 5.1. Investigational Product and Other Study Treatment

**Table 7 Study treatment and Challenge agent table**

	Study Treatment		
Product name:	0.5% GSK2646264	1% GSK2646264	Placebo
Formulation description:	White to off white aqueous cream	White to off white aqueous cream	White to off white aqueous cream
Dosage form:	Topical	Topical	Topical
Unit dose strength(s)/Dosage level(s):	0.5% (w/w)	1% (w/w)	NA
Route/ Administration/ Duration:	Topical; ; SINGLE USE BOTTLES ONLY	Topical; ; SINGLE USE BOTTLES ONLY	Topical; ; SINGLE USE BOTTLES ONLY
Dosing instructions:	Should be applied topically as directed.	Should be applied topically as directed.	Should be applied topically as directed.
Physical description:	White-to-off-white aqueous cream stored in amber glass jars	White-to-off-white aqueous cream stored in amber glass jars	White-to-off-white aqueous cream stored in amber glass jars
Manufacturer/ source of procurement:	Medpharm Guildford	Medpharm Guildford	Medpharm Guildford

Each bottle of cream is for single use only.

	Challenge Agent Treatments						
Product name:	Dermatophagoides pteronyssinus	Timothy Grass Pollen	Cat dander	Birch pollen	Positive Control	Negative Control	Mixed Grass Pollen
Formulation description:	Solution for skin prick test						
Dosage form:	Cutaneous						
Unit dose strength(s)/Dosage level(s):	0.003 microlitres						
Route/ Administration/ Duration:	Cutaneous						
Dosing instructions:	Superficial layer of skin is pierced with an ALK lancet perpendicular to the skin.	Superficial layer of skin is pierced with an ALK lancet perpendicular to the skin.	Superficial layer of skin is pierced with an ALK lancet perpendicular to the skin.	Superficial layer of skin is pierced with an ALK lancet perpendicular to the skin.	Superficial layer of skin is pierced with an ALK lancet perpendicular to the skin.	Superficial layer of skin is pierced with an ALK lancet perpendicular to the skin.	Superficial layer of skin is pierced with an ALK lancet perpendicular to the skin.
Physical description:	Solution for skin prick testing						
Manufacturer/ source of procurement:	ALK-Abello A/S						

## 5.2. Challenge Agents

### 5.2.1. Skin prick test allergens

A solution of each challenge agent will be applied using the skin prick method as described in The Global Allergy and Asthma European Network (GA2LEN) guidelines ([Heinzerling](#), 2013). This is a widely accepted method used in allergy clinics to test for histamine and allergen sensitivity; causing pruritus, skin flare and a skin wheal. The skin prick method involves placing a drop of histamine or allergen solution onto the skin and using a lancet to gently pierce the superficial layer of the skin. The excess histamine or allergen solution is then wiped away.

**The following challenge agents will be used as allergens as part of the skin prick test. Full details are listed in the table in Section 5.1**

- **mixed grass pollen,**
- **Dermatophagoides pteronyssinus,**
- **birch pollen,**
- **cat dander**
- **positive control – histamine**
- **negative control – saline**

## 5.3. Medical Devices

Not applicable.

## 5.4. Treatment Assignment

Subjects will be assigned to treatment in accordance with the randomization schedule generated by Parexel, prior to the start of the study. Randomisation will occur within each cohort of study. Subjects will be randomised to 1:1 to receive bilateral treatment of GSK2646264 or placebo in Part A. For Parts B & C, subjects will be randomised 3:1 active:placebo respectively, to receive either GSK2646264 or placebo.

## 5.5. Planned Dose Adjustments/Progression and Stopping criteria

The study will enrol 1 sentinel subject for Part A dosing group 1 and, Part A dosing group 2. Each sentinel subject will be dosed 1 day at least before any other subjects of their dosing group or cohort. Please refer to Section 5.6 and Section 5.7 for dose adjustments and stopping criteria.

This protocol allows some alteration from the currently outlined dosing schedule, but the maximum topically applied dose at any one time will be 10mg/cm^2 of cream (360mg of free base drug) over 3600 cm^2 (20% BSA) with, based on preclinical modeling, a 6 fold cover compared to the predicted Cmax at the NOEL (16 ng/mL) and 3.5 fold cover

compared to the predicted AUC at the NOAEL (220 ng.hr/mL), or the dose which will provide this Cmax and this AUC (See Section [3.2.2](#)).

The GSK review team will be unblinded to the randomisation code and will usually include the GSK pharmacokineticist, GSK statistician, GSK data management, GSK medical monitor, GSK study team leader, GSK Global Clinical Safety and Pharmacovigilance and GSK Clinical Matrix Team leader. Other GSK employees may be included in discussions around dose adjustments and progression if it is deemed necessary and relevant by the above mentioned team members.

The Investigator or designee, study co-ordinators and any other unit staff who have been involved in assessing subjects will remain blinded during the study; however, they will attend the start of each review meeting to update the GSK team on safety and tolerability summary from each cohort; these team members will not be part of the unblinded dose escalation discussions. The investigator and/or designee should send the relevant data to the GSK review team prior to the meeting of the Safety Monitoring Committee (SMC). The study monitor will remain blinded.

The SMC will consist of the GSK review team and the Investigator and/or designee. The SMC will:

- Approve escalation from dosing group 1 to dosing group 2 in Part A (See Section [5.5.3](#))
- Approve the selection of dosing regimen to be used in Parts B and C (See Section [5.5.3.2](#))
- Evaluate and confirm potential dose-limiting toxicities
- Pause enrolment and/or request safety-related changes to the trial protocol.

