### **3.2.2.2. Additional preliminary data from Part A**

Preliminary human PK data from Part A (up to 1% strength, up to 10% BSA) demonstrated a geometric mean  $C_{max}$  after 4 days dosing of 5.59 ng/ml, providing a margin of 2.8 in comparison to the  $C_{max}$  NOEL achieved (~16ng/ml). After 4 days of dosing the geometric mean  $AUC$  was 103.8 ng·h/ml, allowing a 2.1 fold systemic margin compared to the  $AUC_{(0-t)}$  at the NOAEL.

This allows 3 days dosing at 1% strength, 10% BSA for Part B. For further progression of dosing in parts B and C refer to Section [5.5.3.3](#).

Further predictive modeling using the data from Part A, but with no inclusion of elimination rate, suggests that coverage of 10% BSA using the 1% cream over 7 days of dosing would lead to an estimated  $C_{max}$  of 10.12ng/ml and an  $AUC$  of 219.8ng·h/ml.

The information in the above paragraph is superseded by the information in Section [3.2.2.3](#).

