### **3.2.2.3. Additional preliminary data from Part B**

A population pharmacokinetic model integrating all plasma data from part A and the preliminary data from n=4 in part B lead to an estimation of the half life of 57 hours for GSK2646264. This model shows that in order to maintain a 1.8 fold margin with the  $AUC$  NOAEL to allow women of child bearing potential in the trial the doses of 180mg (10% BSA) should be administered every three days, over a total 7 day duration, rather than every day.

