#### **5.5.3.4. Progression within Part C**

Dosing in Part C will only commence once relevant data from the first four subjects in Part B have been reviewed, (see Section 5.5.3.3) to allow greater confidence in predictions of the pharmacokinetics in Part C. The BSA over which study treatment will be administered in Part C is anticipated to be 10%, but is subject to change if appropriate based on preliminary data from Part B. However, the maximum BSA will not exceed 20%.

The first four subjects of Part C will be randomised so that one of the four subjects will receive placebo and the three other subjects will receive GSK2646264. An informal review of the preliminary data from the first 4 subjects may be conducted after they have completed the study. PK, safety and tolerability data up to and including the follow-up visit, will be reviewed by the Sponsor. If required, a discussion with the SMC regarding any changes or adjustments to the dosing regimen in Part C will be held. Recruitment of the full planned cohort (n=16) may continue during any data review. The dosing regimen or study population may be adjusted as appropriate after this interim review for the rest of the subjects in Part C..

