#### **5.8.1. Adjusting dose/ stopping dose escalation**

If (cohort's average) predicted or observed  $C_{max}$  or  $AUC(0-24\text{ h after last dose})$  of GSK264624 is greater than 16 ng/mL or 220 ng.hr/mL, respectively, doses for subsequent cohorts may be adjusted based on tox cover and will need to be decided by the SMC but will not exceed agreed margins.

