### **Calculation of Predicted human exposure**

The rate of penetration values are in effect the dose of GSK2646264 which reaches the systemic circulation per cm^2 per hour. We assumed that the rate of penetration remains constant over a 24 hour period and thereby acts like a constant infusion into the blood.

The dose in 24 h is therefore reliant on the surface area covered by the cream formulation. We have assumed 10% body surface area coverage on a 70 kg human (1.8 m^2) which is therefore 1800 cm^2.

$$\text{Dose in 24 h} = \text{Penetration Rate} * 24 * 1800$$

The flux determined for the creams and the predicted human PK parameters (CLb: 13 mL/min/kg, Vss: 0.8 L/kg) were used to predict the Cmax and AUC0-24h when applying the creams to the different BSA in the clinical study. Predictions were performed in WinNonlin (Phoenix v6.3.0.395) using an IV infusion model.

The derived Cmax and AUC were converted to plasma using the human blood:plasma ratio of 0.7 and also displayed corrected for fraction unbound using a human Fup of 1.05%. The calculated values are displayed below and in Section 3.2.2.1 of the protocol.

Formulation strength	BSA %	Plasma Cmax (ng/mL)	Plasma AUC (ng.h/mL)
Arlacel - 0.5%	0.2	0.01	0.31
	1	0.06	1.56
	5	0.32	7.79
	10	0.64	15.57
	20	1.29	31.14
Arlacel - 1%	0.2	0.03	0.61
	1	0.13	3.07
	5	0.64	15.36
	10	1.29	30.71
	20	2.57	61.43
Fraction unbound corrected			
Arlacel - 0.5%	0.2	0.000	0.00
	1	0.001	0.02
	5	0.003	0.08
	10	0.007	0.16
	20	0.013	0.33
Arlacel - 1%	0.2	0.000	0.01
	1	0.001	0.03
	5	0.007	0.16
	10	0.013	0.32
	20	0.027	0.64

Formulation strength	BSA %	Plasma Cmax (ng/mL)	Plasma AUC (ng.h/mL)
Arlacel - 0.5%	0.2	0.01	0.31
	1	0.06	1.56
	5	0.32	7.79
	10	0.64	15.57
	20	1.29	31.14
Arlacel - 1%	0.2	0.03	0.61
	1	0.13	3.07
	5	0.64	15.36
	10	1.29	30.71
	20	2.57	61.43
Fraction unbound corrected			
Arlacel - 0.5%	0.2	0.000	0.00
	1	0.001	0.02
	5	0.003	0.08
	10	0.007	0.16
	20	0.013	0.33
Arlacel - 1%	0.2	0.000	0.01
	1	0.001	0.03
	5	0.007	0.16
	10	0.013	0.32
	20	0.027	0.64

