## 12.6. Appendix 6: Comparison Of Predicted Human Plasma Exposures To Animal Safety Studies

[figure not shown]
			MABEL		Human WB CD69 IC 20 : 1150 ng/mL			Exposure with 1% cream (20% BSA) expected 447- fold lower than the IC 20 .		
Human predicted PK parameters			Clearance ( in vivo CL b )			13 mL/min/kg (60% LBF)			IVIVE	
			Volume (V ss in human)			0.8 L/kg			Single species scaling. Rat V ss corrected for species Fub diff. (Obach, 1997)	
			Half-life			0.7h			Estimated from CL b and V ss	
	C max (ng/mL)	AUC (ng.h/mL)	Dose (mg/cm  ) [mg of free drug]	%BSA [cm  ]	Predicted margin to NOEL C max (thyroid finding)	Predicted margin to NOAEL AUC (0-t) 3% dermal	Predicted margin MABEL IC 20	Predicted margin to C max NOAEL (EFD findings)	Predicted margin to AUC NOAEL (EFD findings)	
Rat (0.5% strength)	1.4 - 6.6	15.3 - 57	20-44 [4.1-9.0]	10%	NA	NA	NA	NA	NA	
Pig (0.5% strength)	1.9 - 47	20 - 118	43 [8.7]	10%	NA	NA	NA	NA	NA	
Human Starting dose 0.5% strength (predicted)	0.01	0.31	10 [1.8]	0.2% [36]	1600	700	115,000	16,700	719	
Human Highest dose group 1 and CU 0.5% strength (predicted)	0.32	7.8	10 [45]	5% [900]	50	30	3600	521	28.5	

	Cmax (ng/mL)	AUC (ng.h/mL)	Dose (mg/cm  ) [mg of free drug]	%BSA [cm  ]	Predicted margin to NOEL Cmax (thyroid finding)	Predicted margin to NOAEL AUC (0-t) 3% dermal	Predicted margin MABEL IC 20	Predicted margin to Cmax NOAEL (EFD findings)	Predicted margin to AUC NOAEL (EFD findings)	
Human Highest Dose Group 2 and CsU 1% strength (predicted)	2.57	61.4	10 [360]	20% [3600]	6	3.5	447	65	3.6	
Human Highest Dose Group 2 and CsU 1% strength dib (predicted)	2.57	61.4	10 [720]	20% [3600]	3	1.75	224	32.5	1.8	
Systemic levels in human predicted using the maximum observed penetration rates for each cream strength (0.5 and 1%) and predicted human PK parameters. (IVIVE: in vitro - in vivo extrapolation).										
Application of the 1% and 0.5% creams (10 mg/cm  ) are expected to produce dermal concentrations above the IC90 as determined by the in vitro skin penetration and ex vivo histamine release assays.										

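### The 20% BSA (360 mg) ceiling left open for Part C still rests on preclinical 6-fold and 3.5-fold margins that the protocol's own human PK no longer supports, and it is not reconciled with the 1.8-fold AUC margin in Section 3.2.2.3

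*Protocol*

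**What the plan says.** The ceiling and its support appear in several places. Section 5.5 allows up to 360 mg over 3600 cm² (20% BSA), "with, based on preclinical modeling, a 6 fold cover compared to the predicted" Cmax at the NOEL of 16 ng/mL, and 3.5-fold cover "compared to the predicted AUC at the NOAEL (220 ng.hr/mL), or the dose which will provide this Cmax and this AUC". The Section 3.2.2 summary gives the same two margins. Section 3.2.2.1 applies the 6-fold figure to Parts A and C, and Appendix 6 tabulates both.

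The human data come in two later subsections. Section 3.2.2.2 reports Part A exposure after four days at up to 10% BSA: Cmax 5.59 ng/mL with a margin of 2.8, and AUC 103.8 ng.h/mL, "allowing a 2.1 fold systemic margin compared to the" AUC at the NOAEL. Section 3.2.2.3 gives a population-model half-life of 57 h and concludes that, "in order to maintain a 1.8 fold margin with the $AUC$ NOAEL to allow women of child bearing potential in the trial", 180 mg (10% BSA) should be given every three days and not daily.

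Part C is planned at 10% BSA. Sections 3.1.5 and 5.5.3.4 make that subject to change on preliminary data; the latter adds "However, the maximum BSA will not exceed 20" per cent. Section 5.8.1 sets PK limits of 16 ng/mL and 220 ng.h/mL on the cohort's average predicted or observed exposure. Doses beyond those limits "will need to be decided by the SMC but will not exceed agreed margins".

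**The concern.** A margin quoted in support of a dose ceiling is what a reviewer would use when deciding whether to move towards that ceiling. Here the quoted margins describe a model that the trial has since tested in people. Observed exposure was several times the prediction, at no more than half the ceiling area. The statement in Section 3.2.2.2 that its information is superseded covers only the seven-day projection just above it, so the 6-fold and 3.5-fold figures remain current text.

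The 1.8-fold AUC margin is the protocol's stated reason why women of child-bearing potential can take part at 180 mg every three days. Section 4.3.1.1 allows them into Parts B and C. Section 9.3.1.3 lets a sponsor review change the Part C regimen, with SMC discussion only if required. An area increase permitted by Sections 3.1.5 and 5.5.3.4 could therefore lose the margin in Section 3.2.2.3 while the ceiling text still reports 3.5-fold cover.

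**Working it through.** Margin = limit / exposure. The limits are 16 ng/mL (Cmax) and 220 ng.h/mL (AUC), from Sections 5.5 and 5.8.1.

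**1. Reproduce the plan's figures.** Appendix 5 says: "The flux determined for the creams and the predicted human PK parameters (CLb: 13 mL/min/kg, Vss: 0.8 L/kg) were used to predict" exposure, treating the flux as a constant infusion. For 1% cream the flux is 27.17 ng/cm²/h; body weight is 70 kg and the blood:plasma ratio 0.7. At 3600 cm²:
- plasma Cmax = 27.17 × 3600 / (13 × 70 × 60) / 0.7 = 2.56 ng/mL (Appendix 5: 2.57)
- AUC over 24 h = 2.56 × 24 = 61.4 ng.h/mL (Appendix 5: 61.43)
- margins = 16/2.57 = 6.2 and 220/61.43 = 3.58, matching the stated 6 and 3.5.

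**2. Compare with the human data.**
- Margins at up to 10% BSA: 16/5.59 = 2.86 and 220/103.8 = 2.12 (stated 2.8 and 2.1).
- Observed over predicted for 10% BSA: 5.59/1.29 = 4.3 (Cmax) and 103.8/30.71 = 3.4 (AUC).
- Half-life: predicted ln 2 × 800 / 13 / 60 = 0.71 h; estimated 57 h. A 0.7 h half-life implies almost no carry-over between daily doses, so the 24 h prediction is also the model's prediction for day 4.

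**3. Carry the 1.8-fold margin to the ceiling.** If 1.8 is the margin reached at 180 mg every three days, the AUC there is 220/1.8 = 122.2 ng.h/mL.
- Proportional to area, as in Appendix 5: 2 × 122.2 = 244.4; 220/244.4 = 0.90.
- AUC proportional to dose^0.75: 1.8/2^0.75 = 1.07. To dose^0.5: 1.8/2^0.5 = 1.27.
- Under proportionality, keeping 1.8 at 360 mg needs an AUC of 220/3.6 = 61.1 or less at 180 mg, half of what 1.8 implies.
- If 1.8 refers to the embryofetal AUC NOAEL, Appendix 6 implies 3.6 × 61.43 = 221 ng.h/mL, so nothing changes.

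**4. Check by superposition.** Assume one compartment, a 57 h half-life, and 103.8 as the AUC over 24 h after the fourth daily dose. The daily carry-over is r = exp(−24 ln 2/57) = 0.747. Doses on days 1, 4 and 7 give a factor of 1 + r³ + r⁶ = 1.590. The AUC per 10% BSA dose is 103.8 divided by the sum of the four daily areas (in units of 10% BSA), each weighted by r to the number of days before day 4.
- Protocol Table 3 areas (0.52, 0.52, 0.5, 0.5): 103.8/1.380 = 75.2. The AUC is 119.6 at 180 mg (margin 1.84) and 239.2 at 360 mg (margin 0.92).
- SAP Table 12 areas (0.52, 0.52, 1, 1): 103.8/2.254 = 46.1. The AUC is 73.2 at 180 mg (margin 3.0) and 146.5 at 360 mg (margin 1.50).
- 10% BSA of active cream on all four days, which neither table shows: margin 1.81 at 360 mg.

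**5. Results for 360 mg side by side.**

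| Basis | AUC (ng.h/mL) | Margin |
|---|---|---|
| Stated, preclinical | 61.4 | 3.5 |
| From 1.8, proportional | 244 | 0.90 |
| From 1.8, dose^0.75 | 206 | 1.07 |
| From 1.8, dose^0.5 | 173 | 1.27 |
| Superposition, protocol Table 3 | 239 | 0.92 |
| Superposition, SAP Table 12 | 146 | 1.50 |
| Part A AUC doubled (four daily doses, not the Part C schedule) | 208 | 1.06 |

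**6. Check the limits.** Reaching 220 is a margin of 220/220 = 1.0. A mean AUC between 122 and 220 has lost the 1.8-fold margin without reaching the Section 5.8.1 limit.

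**The case against.** The strongest reply has five parts.

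- **The margins are labelled preclinical and are computed correctly.** This stands. A reader might infer an arithmetic error, but step 1 rules it out. Appendix 6 is presented as a table of predictions and reports them faithfully.
- **20% BSA is an outer bound, and recorded reviews have been cautious.** Also true. Part A group 2 was cut to four days, Part B to 3.5% BSA, and Part C to every three days. This lowers the chance of a move to 20% but does not update the figures that would support one.
- **Section 5.8.1 acts on predicted as well as observed exposure.** Correct, so a prediction of 244 would itself trigger it. It would be wrong to say the limit could not catch that case. Section 5.8 also lets dosing be halted or adjusted whenever judged necessary. Neither provision states 1.8, and the range from 122 to 220 remains uncovered.
- **Section 5.5 has an exposure-based alternative to the fixed ceiling.** It does, but the exposure it names is 16 and 220, again a margin of 1.0 on its plainest reading.
- **The margins mentioned in Section 5.8.1 may be those of Appendix 6.** Section 5.5.3.3 points there, and the lowest AUC margins listed are 1.75 and 1.8. On that reading, doubling the area at the cost of 1.8 is already barred. The reading is plausible, but Appendix 6 lists many margins, all preclinical predictions, and Section 5.8.1 names none.

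The scaling to 20% BSA is also unverified. The population PK output is not in the documents, and area-proportionality comes from the model whose predictions failed.

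**Conclusion.** The inconsistency is real and bears on a decision figure. The 6-fold and 3.5-fold margins at the ceiling cannot stand unqualified beside observed margins of 2.8 and 2.1 at up to 10% BSA and a half-life of 57 h. That much needs no extrapolation.

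Loss of the 1.8-fold margin at 360 mg every three days is conditional. It is about 0.9 if exposure is proportional to area and 1.8 is the margin reached at 180 mg. Less-than-proportional exposure gives about 1.1 to 1.3, and the SAP Table 12 areas about 1.5. All fall below 1.8. The SAP areas give 3.0 at 180 mg and so do not reproduce the stated 1.8; the protocol Table 3 areas do (1.84). That disagreement between the two tables is a separate issue.

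A reader might infer that 20% BSA would exceed 220 ng.h/mL. The documents do not support that as a certainty: the estimates run from 146 to 244, and only the proportional and Table 3 bases cross the limit.

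**What to change.** - In Sections 3.2.2, 3.2.2.1 and 5.5, state the margins at the ceiling from the observed Part A and Part B PK and the population model, with the dosing schedule and treated area they assume.
- Keep the Appendix 6 predictions, label them as superseded, and put the observed margins beside them.
- Reconcile Sections 3.1.5, 5.5, 5.5.3.4 and 5.8.1 with Section 3.2.2.3 so that one stated margin governs Part C dose changes, and give that number in Section 5.8.1.

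Which ceiling and which margin apply is for the sponsor and SMC to decide. The cost is amendment wording, using PK data and a model the sponsor already holds. The stated margins become less favourable. No new patients or procedures are needed.
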